DBS has been well established as a treatment for Parkinson's disease, essential tremor, dystonia, and OCD, and has achieved full approval, or a humanitarian device exemption for each of these indications.[8-18] There have been many DBS studies and position papers detailing careful and meticulous techniques for screening patients[19-21].

DBS, though a minimally invasive therapy, still has associated risks, and DBS failure can result in medical complications and this endpoint can have economic consequences[22]. Patient selection and management can likely improve the risk-benefit ratio for individual sufferers and this will likely apply to TS DBS[23]. The importance of pre-operative assessment, patient selection, DBS team expertise, DBS team experience, and post-operative management has been shown to be important,

especially when groups have studied cohorts of patients that have been DBS failures[22, 23]. Since TS is a childhood onset disorder, often with complex clinical features, a waxing and waning course, and frequent neuropsychiatric comorbidities[5], the evaluation of patients has a level of complexity greater than many of the other current DBS indications[23]. During the evaluation period there is also a risk that tics may be falsely under- or over-quantified due to frequent changes in tic manifestations, and effects of social context. The first attempted surgeries for TS were ablations (i.e. lesions) placed in the thalamus and these were performed by Hassler and Dieckmann[24]. In 1999, Visser-Vandewalle reported the first case of thalamic DBS for TS[25]. Since this report, multiple groups have observed improvement with DBS despite utilizing many brain targets and many approaches[25-43].

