listed in the schedule of assessments are not necessary at every visit, with the exception of the C-SSRS. Subjects will be interviewed using the YGTSS at screening and one day prior to implantation we will recheck YGTSS to be sure they continue to meet eligibility criteria. The MRTRS will be videotaped, and blinded review will be performed by two movement disorders neurologists at baseline and at 6 months. The blinded reviewers will examine videotapes from baseline and six months in chronic continuous stimulation, OFF DBS, and responsive conditions. Additionally the study psychiatrist, assisted by the study coordinator, will perform baseline, Month 6, Month 12, Month 18 and Month 24 follow-up visits including the HAM-D, Y-BOCS, YMRS, QOLAS, SF-36, C-SSRS and CAARS (as necessary) (follow-ups to be performed +/- 14 days). The neuropsychology battery will also be obtained by the study neuropsychologist pre-surgery and approximately one year post-surgery. The C-SSRS will be administered at each study visit by the study neurologist or psychiatrist to monitor for suicidal ideation and/or intent. Along with these assessments, there will be careful documentation of all adverse events and concomitant medications therapy (reporting any medications the patients may have taken that were not allowed by protocol). At any time, participants may request to be seen for an “unscheduled visit,” for example, to assess programming parameters or address an adverse event. It will be up to the principal investigator’s discretion which assessments to perform at unscheduled visits. For an overview of the study procedures and timepoints, the Schedule of Events is included below.

Schedule of Events

Study Events per ICF and Protocol (monthly visits to occur +/- 14 days, except month 1, which will occur +/- 7 days) **	Screening	Baseline	Bilateral Lead Implants***	IPG Implant ***	Thresholds	Month 1	Month 2	Month 3	Month 4	Month 5	Month 6	Visits 6.1 - 6.4*	Month 12	Month 18	Month 24	Follow up visits
Informed Consent	X															
Medical History (included in each consult as applicable)	X	X****														
Neurology Exam	X															
Physical Exam (included in each consult as applicable)	X	X****											X		X	
Vital Signs	X	X			X	X	X	X	X	X	X		X	X	X	
Collection of Urine Samples	X															
Urine Pregnancy Test	X	X****														
Drug Test	X	X****														
Psychiatric Exam	X															
Neuropsychologist Exam	X												X			

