Demographics (age, disease duration, family history, smoking history, alcohol history and substance abuse history)	X															
Structured Clinical Interview for DSM-V (MINI)	X															
Yale Global Tic Rating Scale (YGTSS)	X	X				X	X	X	X	X	X	X	X	X	X	X
Blinded Yale Global Tic Rating Scale (YGTSS)	X											X				
Pre-Implant Modified Rush Tic Rating Scale (MRTS)	X															
Modified Rush Tic Rating Scale (MRTS) with device turned on, off, and "responsive" setting						X	X	X	X	X	X	X	X	X	X	X
Blinded Rating Modified Rush Tic Rating Scale (MRTS)	X											X				
SF-36® Health Survey	X					X	X	X	X	X	X		X	X	X	
Hamilton Rating Scale for Depression (HAM-D)	X											X		X	X	X
Yale-Brown Obsessive-Compulsive Scale (Y-BOCS)	X											X		X	X	X
Young Mania Rating Scale (YMRS)	X											X		X	X	X
The Conner's Attention Deficit Questionnaire (CAARS)	X											X		X	X	X

Neuropsychological Battery (Weschler abbreviated scale of intelligence, digit span and spatial span, California Verbal Learning Subtest, Story and Face Memory Subtest of WMS-III, Judgement of Line Orientation, Stroop Test, Trailmaking Test, Word Fluency Test, Grooved Pegboard, State Trait Anxiety Inventory, Beck Depression Inventory II)	X													X			
Premonitory Urge for Tics Scale (PUTS)	X	X				X	X	X	X	X	X	X	X	X	X	X	X
Columbia Suicide Severity Rating Scale (C-SSRS)	X	X				X	X	X	X	X	X	X	X	X	X	X	X
Physiology Collection		-			X	X	X	X	X	X	X	X	X	X	X	X	X
Quality of Life Assessment Schedule (QOLAS)	X											X		X	X	X	
Review of Inclusion/Exclusion Criteria	X	X															
Review by multi-disciplinary DBS panel	X																
Neurosurgical Exam, including co-morbidities, risk assessment	X																
MRI brain w/dye			X														
CT scan for localization				X													
Anesthesia				X													
Hospitalization			X														
Device Activation					X												
Device Programming						X	X	X	X	X	X	X	X	X	X	X	X
Explant																	X
Replacement procedure (either new battery or non-IDE DBS)																	X
Concomitant Medication Log	X	X			X	X	X	X	X	X	X	X	X	X	X	X	
Adverse Event Log		X			X	X	X	X	X	X	X	X	X	X	X	X	

* Visits 6.1-6.4 will be up to one month at a time (+/- 14 days), for up to 4 months, at a time point approved by the Principal Investigator between Month 6 and Month 36, based on the individual's response to acute responsive stimulation. If they occur beyond month 24, they make take the place of the follow up visits.

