Subjects will have a post-operative CT scan for lead location and to assess for intracranial air and hemorrhage. The CT scan will be fused back to the MRI. Each of the four contacts on each deep DBS lead will be measured, and localized on an atlas to confirm the correct lead position. In the future if an experimental fMRI or MRI is considered, FDA and IRB approval will be sought. The Summit system has not been evaluated for MR compatibility.

11) Specific Approaches for Specific Aim 1 Overview: The study will follow a prospective blinded design (see Figure 1 below). Effectiveness, tolerability, and safety will be assessed, and the study will allow for exploration of appropriate programming parameters.

12) Study Summary: Once subjects have been consented, baseline measures must be collected within two weeks of the surgery. Subjects will be followed with standardized measures for a minimum of 24 months (+/- 14 days) post-DBS implantation and a maximum of 36 months (+/- 14 days) post-DBS implantation for the research study. The main outcomes will be measured at 6 months post-DBS (+/-

14 days). There will then be three additional days of data collection where subjects will be either “on” DBS, “off DBS” or “on DBS responsive mode (Figure 1 and 2).” MRTRS scales will be collected in each mode for an independent video review. Stimulators will be blindly set to the “mode” for the day and left in that mode for one hour prior to data collection which will include MRTS and also physiology as recorded by the neurostimulator.

[figure not shown]

Figure 1. Study design

- Following recruitment and multidisciplinary screening, candidates will receive bilateral CM DBS plus bilateral ECOG strips, and bilateral chest implanted neurostimulators.
- Prior to implantation, primary outcome and secondary outcome variables will be assessed. A blinded videotape will be obtained of the MRTRS. The blinded videotapes will be evaluated by two blinded movement disorders neurologists who will score the MRTRS's at baseline and 6 months (+/- 14 days).
- Implantation will be accomplished by a neurosurgeon and neurologist, both of whom will not participate in the blinded evaluations of subjects.
- The primary effectiveness outcome for the study will be $\geq 40\%$ reduction on

the blindly rated YGTSS total motor/phonic tic sub-scale at six months on DBS as compared to pre-op baseline. The secondary effectiveness variable will be assessed by the MRTRS blinded ratings.

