- The primary safety outcome will be defined as the serious adverse event (SAE) rate in patients compared to the SAE rate in patients implanted with the Medtronic DBS device for treatment of Parkinson's disease as drawn from published randomized studies[13, 67-71]. The intent is to show that the serious adverse event rate will not exceed the 95th percent confidence interval for the historical experience with the Medtronic DBS for Parkinson's disease. A 95% confidence interval for the SAE rate will be utilized for an analysis of data for 10 subjects at their three month visits due to the small sample size.
- The secondary outcome measure will consist of a review of the types, duration and frequency of non-serious adverse events. Therefore, all adverse events will be used as an additional measure in determining safety outcomes.
- The safety experience will be reviewed approximately every 6 months by the Data Safety Monitoring Board (DSMB). The DSMB will be informed of all serious adverse events and all mild adverse events which are potentially device related. The DSMB will designate each AE as mild or severe; as device related, uncertain to be device related or not device related; and as anticipated or unanticipated. The DSMB may employ a stopping rule for greater than 1 device related death or completed suicide.

Details of the Protocol:

- Following consent, subjects will be screened by the multidisciplinary team

and ethics panel to be certain all inclusion and exclusion criteria are met.

- Following approval by the multidisciplinary and ethics panel, subjects will undergo baseline studies and within four weeks will receive bilateral CM devices and bilateral ECOG devices.
- Stimulation will be turned on within one week (+/- 7 days) after the implant completion which will be approximately one month post lead implantation.
- All subjects will undergo once a month programming visits for months 1-6 (+/- 14 days, with the exception of Month 1, which has a +/- 7 day window). Additional visits may be needed to obtain optimization of settings.

Physiological data will be collected from both the CM thalamus and the ECOG strips during all protocol visits, and responsive parameters will also be tested. Subjects may also choose to come to the clinic for “unscheduled visits” as they deem necessary. The activities done at these visits will be at the discretion of the principal investigator.

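### The visit table puts the only blinded pre-operative tic ratings at Screening, the text puts baseline near surgery, and no section names the score from which the 40% reduction is measured

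*Combined protocol and SAP*

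**What the plan says.** Section 12 (Study Summary) defines the primary effectiveness outcome as a reduction of at least 40% on "the blindly rated YGTSS total motor/phonic tic sub-scale at six months on DBS as compared to pre-op baseline". Section 13 likewise compares six months with the pre-operative value. Neither section names the visit or the rater that supplies that value.

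The Schedule of Events in section 8 has separate columns for Screening and Baseline. Three rows have their only pre-operative mark under Screening: "Blinded Yale Global Tic Rating Scale (YGTSS", "Pre-Implant Modified Rush Tic Rating Scale (MRTS" and "Blinded Rating Modified Rush Tic Rating Scale (MRTS". The YGTSS row that is not labelled blinded is marked at both visits. A footnote repeats history, physical examination, pregnancy test and drug test at Baseline when Screening was more than 30 days before surgery. The blinded tic ratings do not carry that footnote, and no maximum interval is given.

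The text points elsewhere:

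- Section 12: "baseline measures must be collected within two weeks of the surgery".
- Section 12, Details of the Protocol: "subjects will undergo baseline studies and within four weeks will receive bilateral CM devices".
- Sections 8 and 12: blinded MRTRS scoring is at baseline and six months.
- Section 8: "one day prior to implantation we will recheck YGTSS to be sure they continue to meet eligibility criteria". The stated purpose is eligibility, and this rating is not described as blinded.

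The Schedule of Assessments does not settle the matter, because it merges screening and baseline into one pre-operative column.

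**The concern.** The 40% rule is a ratio, so its denominator is part of the endpoint. Here at least two scores could serve: a blinded one at Screening, and a later one at Baseline that is not marked blinded. The day-before recheck is a possible third. Section 4 warns that "there is also a risk that tics may be falsely under- or over-quantified due to frequent changes in tic manifestations", so these scores need not agree.

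Two things are at stake. First, if the Screening score is used, a systematic change between Screening and surgery is credited to stimulation, and the primary comparison is pre-post in one group with no concurrent control to remove it. Second, staff who work from the visit table would take no blinded YGTSS and no MRTRS video at Baseline. A near-surgery pre-implant video cannot be made after implantation. While the reference score is unnamed, the choice could also be made after the results are known.

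**Working it through.** The plan gives no figure for this point, so there is none to reproduce.

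**Inputs from the documents.** Response is a reduction of at least 40% (sections 12 and 13). Eligibility requires a total tic score of at least 35/50 and a motor subscore of at least 15 (section 6), and the YGTSS is rechecked the day before implantation (section 8). Each of the motor and phonic scores has five items on a 6-point scale (section 7), so with items scored 0 to 5 each runs to 25.

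**Step 1: what the denominator does to the threshold.** Let S be the Screening score and B the score just before surgery. If S is the reference, a responder at six months scores 0.6 × S or less. The fall needed after surgery is therefore 1 − 0.6S/B. If B is the reference, it is always 40%.

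| Scale | S | B | 0.6 × S | Fall needed from B |
|---|---|---|---|---|
| Total | 42 | 36 | 25.2 | 1 − 25.2/36 = 30.0% |
| Total | 40 | 35 | 24 | 1 − 24/35 = 31.4% |
| Total | 45 | 35 | 27 | 1 − 27/35 = 22.9% |
| Total | 50 | 35 | 30 | 1 − 30/35 = 14.3% |
| Motor | 20 | 15 | 12 | 1 − 12/15 = 20.0% |
| Motor | 25 | 15 | 15 | 1 − 15/15 = 0% |

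On the total score the recheck limits pre-surgery change to (50 − 35)/50 = 30%, so such change cannot by itself make a responder. The motor subscore has no such protection. A fall from 25 to 15 is exactly 40% and is still eligible if the phonic score is at least 20. This matters because section 6 and the Aim 1 analysis in section 13 name the motor score as the outcome, whereas sections 7 and 12 name the total.

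**Step 2: how much the responder probability could move.** The documents give no variability, so these are assumptions: usual total score with mean 38 and SD 5, independent visit-to-visit SD 3, both pre-operative scores at least 35, and a true 33% fall after surgery. By simulation:

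| Systematic improvement, Screening to surgery | Responder probability, Screening reference | Responder probability, pre-surgery reference | Difference |
|---|---|---|---|
| 0% | 0.23 | 0.23 | 0 |
| 5% | 0.35 | 0.26 | 0.09 |
| 10% | 0.50 | 0.29 | 0.21 |

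The binomial probability of at least 6 responders in 10, the success rule in section 6, is about 0.10 against 0.02 in the 5% row and about 0.37 against 0.04 in the 10% row.

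**Step 3: the same question with no DBS effect.** Assume a usual score with mean 40 and SD 4, a visit SD of 4 to 8, and a 4-point (10%) improvement before surgery. The responder probability is then 0.005 to 0.10 with the Screening reference and 0.002 to 0.08 with the pre-surgery reference. The ambiguity therefore matters most for subjects with a real but partial improvement, who lie near the 40% line.

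**The case against.** The strongest reply is that the table is not the whole plan. Section 12 requires baseline measures close to surgery, blinded MRTRS scoring is said to be at baseline, and the Details of the Protocol put baseline studies after screening and panel approval. A reader of the table might infer that the sponsor has chosen Screening values. The documents do not support that. They contain a contradiction and an unnamed reference score. This part of the reply stands.

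Two further inferences are tempting and also fail.

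- **Treatment between Screening and surgery inflates the response.** Section 6 has behavioural therapy completed before the protocol starts and botulinum toxin offered before surgery is considered. It requires TS medication to be stable before surgery and throughout the trial. These are entry criteria, not a treatment run-in.
- **Waxing and waning alone inflates it.** In Step 2 symmetric fluctuation adds no excess over the pre-surgery reference, because both scores must be at least 35. Only a systematic change does, and no section gives evidence for 5% or 10%. Section 6 also asks for at least 35/50 over 12 months, not one high visit.

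Other fair points are that 50 to 35 is an extreme case, that the day-before rating is an eligibility check and not a rival definition of baseline, and that the secondary on-versus-off comparison at six months does not use the pre-operative score at all.

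None of this names the denominator, brings a blinded rating to the Baseline visit, or reconciles two weeks with four.

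**Conclusion.** The point holds as a contradiction between table and text together with an undefined reference score for the primary endpoint. It does not show that the trial will be biased. If the table is followed, systematic change between Screening and surgery is counted as response. The possible effect ranges from nil to about 20 points of responder probability over the assumed 0% to 10% improvement, and the true size cannot be found from the documents. On the total score, pre-surgery change can supply at most a 30% fall; on the motor subscore it can supply the full 40%.

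One caution on reading the table: the later mark in the two blinded rows appears under Visits 6.1-6.4 and most likely belongs to Month 6. That looks like a column shift in the extracted text. It does not move the first mark from Screening.

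**What to change.** 1. In the Schedule of Events, mark the blinded YGTSS, the pre-implant MRTRS video and its blinded rating at the Baseline visit. Keep the Screening YGTSS for eligibility.
2. Reconcile the two-week and four-week statements in section 12 with the section 8 schedule, so that one window before surgery is stated throughout.
3. In sections 12 and 13, name the Baseline visit's blinded score as the denominator of the 40% reduction, and say who rates it.
4. For subjects already implanted, the Baseline YGTSS is not marked blinded. Report the responder count against both the blinded Screening score and the Baseline score. Replacing one with the other would mix blinded and unmarked denominators among ten subjects.

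The cost is a schedule and wording amendment: existing ratings move to a visit that already includes a YGTSS. The responder rate may come out slightly less favourable.

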Risk Analysis: The Medtronic Activa RC+S device and Medtronic Model 09130 cortical strip system represents a new therapeutic approach to treating TS. As such, the probable risks and anticipated benefits of this treatment approach must be considered based on information from the literature of deep brain stimulation. This experience suggests that deep brain stimulation has an acceptable risk profile and that anticipated benefits outweigh the probable risks. Kimmelman and colleagues in a recent meta-analysis of deep brain surgery for Parkinson's disease revealed a favorable risk-benefit ratio with the estimated intracerebral hemorrhage rate of 1.57% (95% confidence interval, 1.26%-1.95%), and the proportion of trajectories associated with serious neurological deficits was only 0.41% (0.28%-0.60%)[74].

14) Safety Studies and Potential Risks with the Investigational Device:

Experience with the Medtronic RC+S device and Cortical Strips:

There are currently no human patients implanted with the Medtronic Activa RC+S along with the Medtronic Model 09130 cortical strip for TS.

Safety of Chronically Implanted Neurostimulators: Probable risks associated with chronically implanted neurostimulators and of devices implanted in the cranium include the risks of surgery-related adverse events such as hemorrhage and infection, chronic implantation adverse events such as infection, erosion and necrosis, stimulation-related side effects or discomfort, and stimulation associated brain injury.

Experience from randomized DBS studies for Parkinson's disease suggest a low

overall risk[13, 67-71]. Additionally, a recent expert consensus led by Bronstein et al. reviewed DBS complications[75]. The rates of surgical complications depended on the team and experience and included intracranial hemorrhage, stroke, infection, lead erosion without infection, lead fracture, lead migration, and death. These were all rare complications and the most worrisome overall complication was the possibility of symptomatic intracerebral hemorrhage which was less than 2% at experienced medical centers. Hardware infection was the most commonly reported serious adverse effect and ranged from approximately 5% to 20% among reports in the literature[75].

Safety Experience with Medtronic Summit RC+S device and Cortical Strips in TS

There are no human cases published of the use of this device in TS DBS.

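### With ten subjects the primary safety comparison can only describe the SAE rate, not show it stays within the historical interval, and its three-month cut leaves later SAEs out of that analysis

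*Combined protocol and SAP*

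**What the plan says.** Section 12 (Study Summary) compares the SAE rate in this trial with the rate in published randomized trials of Medtronic DBS for Parkinson's disease. The goal is put as a demonstration: "The intent is to show that the serious adverse event rate will not exceed the 95th percent confidence interval for the historical experience". The method is one sentence, "A 95% confidence interval for the SAE rate will be utilized for an analysis of data for 10 subjects at their three month visits", which ends by giving the small sample as the reason. The next bullet adds non-serious events as a secondary measure and says that all adverse events will inform the safety assessment.

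Other places bear on the same point:

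- Section 7 (Research Plan) repeats the safety outcome without a time point.
- Section 13 (power and statistical methods) has no safety analysis. Ten subjects are justified there on effectiveness only.
- Section 12 puts the main outcomes at six months after DBS. Month 6 data collection may be postponed to as late as 12 months after the Month 1 visit.
- Section 12 (Details of the Protocol) starts stimulation soon after the implant is complete, "which will be approximately one month post lead implantation".
- Section 8 (Schedule of Events) keeps the adverse event log running at visits after Month 3.
- Section 17 has the DSMB meet about every six months until all subjects reach the six-month outcome, and one of its stopping rules is written for the six months after surgery.

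The text available gives no historical SAE rate, interval or follow-up length. It does not say whether the rate counts subjects or events, or which quantity must stay below which limit.

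**The concern.** To show that a rate does not exceed a limit is a non-inferiority type of claim. It needs a stated limit, a rule that says when the claim is met, and enough subjects for the rule to separate acceptable from unacceptable rates. The plan has none of these. With the rule open, it could also be chosen after the data are seen, and the candidate rules behave very differently.

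The window is a second difficulty. Section 12 lets stimulation settings change during months 1 to 5 and then requires 30 days of stable settings before the primary outcome. A three-month safety analysis can therefore close before the settings on which effectiveness is judged are final. The only reason given is the small sample. That does not justify a shorter window, since cutting follow-up removes information from a sample that already has little.

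At stake is the trial's primary safety conclusion, for a device combination that, by Section 14, had no published human cases in Tourette syndrome.

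**Working it through.** The plan states no safety power, precision or margin, so there is no safety figure to reproduce.

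**Inputs.** n = 10 and the 95% level are from Section 12. Three inputs are assumptions: the interval is two-sided (Section 13 makes all tests two-sided); the rate is the proportion of subjects with at least one SAE; and U, the upper end of the historical interval, is varied because it is not given.

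**Step 1: exact (Clopper-Pearson) 95% limits for x/10.** For x = 0 the upper limit is 1 − 0.025^(1/10) = 1 − 0.6915 = 30.8%. The one-sided 95% version is 1 − 0.05^(1/10) = 25.9%.

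| Subjects with an SAE | Exact two-sided 95% CI |
|---|---|
| 0/10 | 0 to 30.8% |
| 1/10 | 0.3 to 44.5% |
| 2/10 | 2.5 to 55.6% |
| 3/10 | 6.7 to 65.3% |

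**Step 2: rule A, the trial's upper limit must fall below U.**

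- U ≤ 30.8%: no result passes.
- U = 40%: only 0/10 passes. Probability 0.8^10 = 0.107 at a true 20%, and 0.9^10 = 0.349 at a true 10%.
- U = 45%: 0 or 1 passes. At a true 10%, 0.9^10 + 10 × 0.1 × 0.9^9 = 0.349 + 0.387 = 0.736.
- U = 60%: up to 2 pass. Probability 0.383 at a true 30%.

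For scale, 80% power under this rule needs 45 subjects for a true 20% against U = 40%, and 107 for a true 10% against U = 20%.

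**Step 3: rule B, the observed rate must not exceed U.** The pass probability is P(X ≤ 10U) with X binomial(10, true rate).

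| Assumed U | Passes with | True rate = U | Higher true rates |
|---|---|---|---|
| 10% | ≤ 1/10 | 0.736 | 0.376 at 20%; 0.149 at 30% |
| 20% | ≤ 2/10 | 0.678 | 0.383 at 30%; 0.167 at 40% |

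**Step 4: rule C, an excess is declared only if the trial's lower limit is above U.** This takes 4/10 at U = 10% (probability 0.12 at a true 20%) and 6/10 at U = 20% (0.17 at a true 40%). Failing to declare an excess would say little.

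**Step 5: the window.** Three of six months is 50% of the nominal period. If the constant hazard is taken as an assumption, the three-month risk is 1 − (1 − six-month risk)^(1/2): six-month risks of 10%, 20% and 30% appear as 5.1%, 10.6% and 16.3%. SAEs that cluster around surgery would make the loss smaller.

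Stimulation time at the cut depends on the time origin. It is about two months if visits count from lead implantation, and about three if they count from activation, which the Schedule of Events places before Month 1.

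**The case against.** A reader might infer that no result could ever meet the safety aim. The documents do not support that. It holds only for rule A with U at or below 30.8%, and they give neither the rule nor U. Above 30.8%, success is possible and sometimes likely, as the 0.736 at U = 45% shows.

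It is also tempting to use Section 14 as the benchmark: "Hardware infection was the most commonly reported serious adverse effect and ranged from approximately 5% to 20% among reports in the literature". That range covers one type of event and comes from an expert review of complications, not from the randomized trials named as comparator. An all-SAE rate in a given population cannot be lower than the rate of one of its components, so 20% is not a ceiling for U.

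A reader might further infer that half of the safety experience is discarded. It is not. SAEs after Month 3 are still logged, reach the DSMB and enter the all-adverse-event review; they are absent only from the primary interval. Six months is the time point of the effectiveness and main outcomes, safety is given its own cut, and the exact fraction lost depends on the time origin and on any postponement.

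Finally, the plan already intends a 95% interval and admits that the sample is small. All of this stands, and it limits the point. It does not supply a limit, a rule or a sizing for the claim, or a reason for the shorter window.

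**Conclusion.** The point holds in this limited form. With ten subjects and no stated historical limit or rule, the primary safety comparison is descriptive and cannot carry the wording of a demonstration. The firm figure is the floor: even 0/10 leaves an exact upper limit of 30.8%. The pass probabilities depend on assumed values of U and the true rate. All the binomial figures assume that subjects, not events, are counted; a rate based on events would need a different interval.

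The three-month cut is unexplained beside six-month main outcomes and a six-month stopping rule. How many SAEs it leaves out of the primary interval cannot be settled from the documents. The changes below alter what the trial can conclude, so this is more than a missing detail.

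**What to change.** In Section 12, and to match in Sections 7 and 13:

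1. Define the primary safety measure as the proportion of all implanted subjects with at least one SAE from lead implantation to a fixed day 180. Keep that day whether or not Month 6 effectiveness collection is postponed, so that the safety window does not lengthen for subjects whose settings take longer to optimize. The three-month figure may stay as supportive.
2. Replace the intent to show non-exceedance with estimation: an exact (Clopper-Pearson) 95% CI beside the historical rate and interval. State those historical figures and their sources, count subjects in the same way, and use a matching follow-up window.
3. State in the plan that 0/10 still leaves an upper limit of 30.8%.

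The cost is a read-out about three months later per subject and a less favourable safety claim. No new data are needed, because adverse events are already logged over this period.
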